- (d) *If the research holds out the prospect of direct benefit to the pregnant woman, the prospect of a direct benefit both to the pregnant woman and the fetus, or no prospect of benefit for the woman nor the fetus when risk to the fetus is not greater than minimal and the purpose of the research is the development of important biomedical knowledge that cannot be obtained by any other means, her consent is obtained in accord with the informed consent provisions of subpart A of this part;*

Consent of the participant is obtained in accord with 45CFR46 subpart A. The consent form is attached with this amendment request.

- (e) *If the research holds out the prospect of direct benefit solely to the fetus then the consent of the pregnant woman and the father is obtained in accord with the informed consent provisions of subpart A of this part, except that the father's consent need not be obtained if*

he is unable to consent because of unavailability, incompetence, or temporary incapacity or the pregnancy resulted from rape or incest.

Not applicable

- (f) Each individual providing consent under paragraph (d) or (e) of this section is fully informed regarding the reasonably foreseeable impact of the research on the fetus or neonate;*

Full information regarding the reasonable foreseeable impact of the research on the fetus or neonate is provided in the informed consent form

- (g) For children as defined in §46.402(a) who are pregnant, assent and permission are obtained in accord with the provisions of subpart D of this part;*

Not applicable

- (h) No inducements, monetary or otherwise, will be offered to terminate a pregnancy;*

No inducements, monetary or otherwise, will be offered to terminate a pregnancy;

- (i) Individuals engaged in the research will have no part in any decisions as to the timing, method, or procedures used to terminate a pregnancy; and*

The investigators will have no part in any decisions as to the timing, method, or procedures used to terminate a pregnancy;

- (j) Individuals engaged in the research will have no part in determining the viability of a neonate.*

The investigators will have no part in determining the viability of a neonate.

X. Recruitment

Endometriosis is a disease unique to women of reproductive age, therefore only women will be recruited and men and children will be excluded. Every effort will be made to recruit eligible women regardless of their race, as endometriosis occurs in all ethnic groups.

NIH employees are permitted to participate. To avoid any appearance of coercion, there will be no direct solicitation of NIH employees by supervisors. Study staff will assure that the participation or refusal to participate will have no effect, either beneficial or adverse, on the subject's employment or position at the NIH,

The study subjects may be recruited through collaborations with the Uniformed Services University of Health Sciences (USUHS), the Walter Reed National Medical Center (WRNMC), and hospitals served by the NICHD Reproductive Endocrinology Fellowship program. In addition, subjects will be recruited through advertising on the NIH Clinical Center Protocol listings, public service announcements, NIH-approved listservs, websites such as Facebook and Twitter accounts,

ResearchMatch. IRB-approved notices may be sent to physicians treating patients with pelvic pain and endometriosis and women's health and endometriosis support and interest groups for sharing with their members via hard-copy, posting, or distributing electronically.

IRB-approved recruitment notices may be posted on physical and electronic bulletin boards at grocery stores, community centers, bookstores, NIH Clinical Center, libraries or placed in advocacy group offices, in doctor's office waiting rooms, libraries, or retail establishments with approval of the venue and in accord with their policy. Flyers may be made available at outreach exhibits, speaking engagements, support group meetings, parent groups, professional meetings, association/trade meetings with approval of the venue and in accord with their policy. IRB-approved advertisements may be placed in electronic and/or local publications such as newspapers, magazines and support or health care organizations, such as the Washington Post, Express, Gazette, Washington Parent, Washingtonian, Bethesda Magazine, Washington Examiner, Military papers, and Washington Jewish Week, Craig's list and in other paid or unpaid advertising venues.

The IRB-approved advertisements will be used in color as submitted, or may be printed in black and white. The color of the ads may vary. Color changes will not be used to change the emphasis of an ad. The size of the ads may vary, but all parts of the ads, including fonts and pictures, will be changed proportionately to the rest of that ad. Disproportionate changes in size will not be used to change the emphasis of an ad.

All advertisements will be sent to the IRB for review.

Subjects will not be compensated for their participation.

XI. Data and Safety Monitoring

As PI, [name], will serve as the IND Sponsor's medical monitor (SMM). The SMM will make the final determinations of relatedness to the investigational product on behalf of the IND sponsor (NINDS). This study will additionally be monitored by the Data and Safety Monitoring Board (DSMB) per NINDS policy. Additional data and safety and quality assurance monitoring will be performed per NINDS requirements. See section XVIII below for the 12-N-0083 monitoring plan.

XII. Technology Transfer

Botulinum toxin for this study is being provided under a grant and Technology Transfer agreement (Letter of Agreement) from Allergan, Inc (Irvine, CA). Allergan is also providing funds for independent study monitoring.

XIII. Conflict of Interest

The NIH guidelines on conflict of interest have been distributed to all investigators. There are no conflicts-of-interest to report. No NIH investigator involved in this study receives any payment or other benefits from Allergan, Inc.

XIV: Informed Consent

Investigators authorized to obtain consent: The following study investigators are designated as able to obtain consent: [name], [name], [name], [name], MD and [name].

Consent process: Participants will have the opportunity to carefully review the written consent form and ask questions regarding this study prior to signing. All participants will receive a verbal explanation in terms suited to their comprehension of the purposes, procedures and potential risks of the study and of their rights as research participants. The consent form will be signed by the participant, a witness and the investigator obtaining consent. The participant will receive a copy of the consent form for her records. The original signed consent form will be sent to the NIH Medical Records Department.

NIH employees and staff who are interested in participating will be given the “NIH Information Sheet on Employee Research Participation” prior to the consent process. Co-workers from the same Branch or Section will not obtain consent from employees.

XV: Travel and Compensation

Compensation for travel for study visits will be provided within the USA in accordance with NIH policy. Overnight accommodations may be provided if necessary.

Participants (including NIH employees) will not otherwise be compensated for participation.

XVI: Qualifications of Investigators

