This will be a double-blinded, randomized, placebo-controlled study to determine if botulinum toxin injection can relieve pain associated with pelvic floor spasm in women with chronic pelvic pain. We plan to study women of reproductive age with pelvic muscle spasm and pain persisting after the surgery for endometriosis. Participating women will be randomly assigned to receive either botulinum toxin or placebo (an inactive salt solution) injection. The group of women receiving placebo will serve as controls. Pregnancy tests will be assessed in women who have not had a hysterectomy at the time of botulinum toxin injection and all women will be advised not to become pregnant in the month following injection. Women will be seen again one month after the first injection to assess the effectiveness of injection. Improvement in pain after the first injection will be assessed for the primary outcome. The women will be followed for a year. All participants will be offered a single reinjection with active drug at the one month visit or later during the 1 year follow-up period if the pain returns.

The intent of this protocol is to evaluate whether botulinum toxin injection improves endometriosis-associated pain as reported by the patient and assessed by gynecology and physiatry. Patients will be seen at baseline study injection, one month after the study injection (4-7 weeks), mid-way through the study (5-8 months) and at the end of the study (11-14 months). With regards to Botulinum toxin injections, patients may receive up to 2 botulinum toxin injections (study injection of botulinum toxin or placebo and then 1 additional active botulinum toxin injection— at the one month visit or later during the year after study injection).

IV. Selection of subjects

A. Inclusion Criteria:

- Female gender
- Age between 18 and 55
- History of endometriosis at surgery
- Persistent pelvic pain for at least 3 months
- Pelvic floor spasm
- Negative pregnancy test (in women who have not had a hysterectomy)
- Willing to use reliable method of contraception for the month after botulinum toxin injection including oral contraceptives, IUD, and barrier with spermicide.
- Willing and able to give informed consent
- Willing and able to comply with study requirements

B. Exclusion criteria:

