- Women with other causes of chronic pelvic pain including infectious, gastrointestinal, psychological disorders, fibromyalgia and chronic fatigue syndrome based on review of medical history within 1 year of first study visit
- untreated severe cervical dysplasia or other gynecologic condition*
- clinically significant abnormalities on physical or laboratory examinations that require evaluation or treatment or that would make participation unsafe.*
- Hysterectomy and bilateral salpingo-oophorectomy
- Pregnancy
- Lactation
- Allergy to albumen or botulinum toxin
- Presence of antibodies to botulinum toxin or loss of response to previous injections for any indication
- A known neuromuscular junction disorder such as myasthenia gravis or Eaton-Lambert syndrome
- History of urinary or fecal incontinence
- Known pelvic prolapse

**Eligibility will be based on a physical exam at NIH at the first study visit, as well as history and available medical records within 1 year before the study visit. Negative test results will be documented to confirm study eligibility. If the Pap and the GC and chlamydia tests were not done outside of the NIH within the previous year, or if documentation of the negative test results is not available, we will await the results of the screening tests done at the NIH before administering the study medication.*

C. Criteria for withdrawal of subjects from the study

- Inability to perform home monitoring or comply with study visit schedule
- Occurrence of an adverse event that precludes further participation in the study at the discretion of the investigator
- Subject wishes to terminate participation

- Incontinence of urine or feces, or pelvic organ prolapse occurring after injection

D. Study discontinuation

- If more than 2 subjects develop incontinence or pelvic prolapse, the study will be discontinued.

V. Study procedures

A. Screening process: Women with at least a three-month history of pelvic pain suggestive of endometriosis and who have a surgical diagnosis of endometriosis will be considered for this study. Eligible women will complete written consent via telephone interview and will complete a baseline screening questionnaire (appendix 1), one month calendar (appendix 2), and submit records confirming surgical diagnosis.

B. Pre-injection medical evaluation:

This will occur in an outpatient area at the Clinical Center and will include the following for all patients:

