 5. Completing of one month's calendar of medication use and baseline pain score and baseline screening questionnaire (Appendix 1 and 2)
 6. Physiatry Assessment for central nervous system sensitization and myofascial dysfunction (Appendix 7)
 7. Patient medication guide: patients will receive the botulinum toxin a medication guide for their review (Appendix 8).

C. Injection Procedure

Eligible women agreeing to participate will be randomized to active or placebo injection. The treating gynecologist, the neurologist performing EMG monitoring, and patient will be blinded to the randomization. Injection will be performed during a clinic visit after study eligibility is confirmed. Patients will be instructed not to change any hormonal treatment of endometriosis for the one month following injection.

One hour before injection, up to 10mg of diazepam will be given orally as an anxiolytic and anesthetic cream (lidocaine 4% cream) placed on the vaginal walls. The gynecologist will perform the injection with sterile technique into areas with palpable spasm, under EMG guidance provided by a neurologist. Patients will receive either 100 U type A Botox® (onabotulinum toxin A) reconstituted with preservative-free saline or a similar volume of saline. The location and amount of toxin/saline injected will be documented using a standardized recording sheet (appendix 9). Patients will be able to leave an hour after injection but will be instructed not to drive until the effects of the sedation have worn off.

Randomization will follow a permuted block design with block sizes of 4 and 6. The Pharmacy Development Service, who will not be blinded, will assign the subject. The toxin or saline will be picked up from the pharmacy and prepared by an unblinded nurse in a private, appropriate clinic area. Syringes with the toxin in solution or saline (which are identical in appearance) will be brought to the treatment room.

On the day of botulinum toxin injections, women who have not had a hysterectomy and who are sexually active will have a urine pregnancy test to exclude pregnancy.

D. Post-injection follow-up

Subjects will be asked to complete a one month's calendar of medication use and pain score after injection.

Subjects will be contacted between 3 days and 2 weeks after injection to monitor for adverse effects including genitourinary infections and change in bowel or bladder function.

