Women who undergo a second injection at the 1 month visit or at any time later within the 1 year follow-up period with the same pretreatment medication, precautions, injection technique, and follow-up as with the first injection. If this injection occurs outside of a scheduled visit, a new baseline will be established to include completion of Standardized Pelvic Pain questionnaire, standardized endometriosis QOL questionnaire, Rome criteria III for Irritable Bowel Syndrome, Painful Bladder Syndrome and PROMIS HRQL measures of sleep, fatigue, anxiety and depression, BPI body territories list, SF 36 Health Survey, Oswestry Disability Score and pain catastrophization scale. All subjects will receive botulinum toxin if a second injection is needed regardless of the randomization group. On the day of botulinum toxin injections, women who have not had a hysterectomy and who are sexually active will have a urine pregnancy test to exclude pregnancy. Women will be asked if they have had urinary or fecal incontinence or pelvic organ prolapse. Those experiencing these symptoms will be systematically assessed and, if significant, will not have an injection. Hormonal treatments and pain medications will be reviewed. One month later, several questionnaires will be completed including: Standardized Pelvic Pain questionnaire, standardized endometriosis QOL questionnaire, Rome criteria III for Irritable Bowel Syndrome, Painful Bladder Syndrome and PROMIS HRQL measures of sleep, fatigue, anxiety and depression BPI body territories list, SF 36 Health Survey, Oswestry Disability Score and pain catastrophization scale. Patients may come for an optional study visit at the one month time point.

Although only the results of the randomized injection will be used for statistical analyses, descriptive data on pain relief will be collected on the outcome of the second injection using the one month calendar of pain and medication use, and botulinum toxin patient response inventory.

F. Mid- and End-Study follow-up

Although only the results of the randomized injection will be used for statistical analyses, descriptive data on pain relief will be collected on the outcome of the additional injection using the one month calendar of pain and medication use, and the botulinum toxin patient response inventory. Additionally, at the mid-way (5-8 months) and study end (11-14 months) study visit,

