At the study visits, women will complete questionnaires describing their amount and frequency of pain, side effects, and the effect of the pain on their quality of life. Some subjects may find these types of questions make them feel uncomfortable. Completing these questionnaires will take about 20 minutes of the patient's time. Evaluation of injection outcome using rating scales may be slightly inconvenient, but presents no medical risk.

2) Transvaginal injection

Transvaginal injection can be painful and can cause bruising. Injection discomfort will be minimized by the use of a topical analgesic applied to the vaginal mucosa and an oral anxiolytic. Sterile technique will be used to diminish the remote risk of infection from injection.

3) Botulinum toxin

Botulinum toxin has been used since 1977 and is considered safe by the American Academy of Neurology, and an NIH-sponsored consensus conference [31, 32]. The main adverse effect associated with botulinum toxin injection is more weakness than intended in the injected or adjacent muscles. Such weakness usually improves within 1-2 months of injection. With pelvic muscle injection, the anal or urethral sphincter could possibly be weakened with resultant incontinence. Sphincter weakness is very unlikely with the dose of toxin to be used here and was not seen in the studies cited above, except in a single woman with known prior urinary incontinence. Women with a history of either bowel or bladder incontinence will be excluded

from this study. If incontinence were to occur, it would be transient, resolving over 3 weeks.

A single case report described an ischiorectal fossa abscess following botulinum toxin injection into the obturator internus and pubococcygeus muscles for refractory pelvic pain. The abscess resolved with intravenous antibiotics, incision and drainage. In that case, the injection was done without ultrasound or EMG guidance to assure needle placement in muscle. To avoid infection and abscess in our patients, the vaginal site of injection will be cleaned prior to injection and EMG guidance will be used each time to assure proper needle placement for intramuscular injection.[33]

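### Section IV.C withdraws a woman from the study for any incontinence or prolapse after injection, which can lose her one-month rating and conflicts with the milder rule in V.E

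*Combined protocol and SAP*

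**What the plan says.** Section IV.C (criteria for withdrawal of subjects from the study) includes "Incontinence of urine or feces, or pelvic organ prolapse occurring after injection". The general adverse-event item in the same list applies only when the event prevents further participation, and leaves the decision to the investigator. The incontinence and prolapse item has neither limit.

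Section V.E (second injection) deals with the same symptoms on the day of a second injection: "Women will be asked if they have had urinary or fecal incontinence or pelvic organ prolapse". It continues: "Those experiencing these symptoms will be systematically assessed and, if significant, will not have an injection".

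Other relevant provisions:

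- **IV.D:** "If more than 2 subjects develop incontinence or pelvic prolapse, the study will be discontinued".
- **V.D:** "Subjects will be contacted between 3 days and 2 weeks after injection to monitor for adverse effects", including changes in bowel or bladder function.
- **III:** the visit that supplies the primary rating is 4-7 weeks after the study injection.
- **V.E:** any second injection is active toxin for everyone, and only the randomised injection enters the statistical analyses.
- **VII.B:** the analysis is by intent to treat and includes data from women who withdraw after randomisation.
- **IX.B.3:** "With pelvic muscle injection, the anal or urethral sphincter could possibly be weakened with resultant incontinence", but "Sphincter weakness is very unlikely with the dose of toxin to be used here". Any incontinence is expected to resolve over 3 weeks.

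**The concern.** Withdrawal from the study and withdrawal from further treatment are different actions, and IV.C specifies the first. The randomised treatment is a single injection that has already been given. The only exposure still avoidable is the second injection, and V.E already controls that.

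What can be lost is the primary outcome. A woman who reports incontinence at the contact between 3 days and 2 weeks meets the IV.C criterion before her 4-7 week rating is due. By the protocol's own account she would probably have recovered by then and could give it. IV.C does not forbid a last rating, but nothing asks for one. VII.B brings data from withdrawn women into the analysis, but it cannot supply a rating that was never taken, and it does not say how a missing one is classified.

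Sphincter weakening is a named possible effect of the toxin, so such losses could be related to arm in a comparison of about 15 women per group. Withdrawal would also end the woman's one-year follow-up, which VII.B gives as the reason for raising the accrual ceiling.

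**Working it through.** **The two rules side by side**

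| | IV.C | V.E |
|---|---|---|
| Trigger | Any incontinence or prolapse after injection | The same symptoms, found significant on assessment |
| Consequence | Withdrawal from the study | Second injection withheld |

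If IV.C governed as written, no symptomatic woman would reach the V.E assessment and its significance test would have no function. The plan does not say which rule prevails.

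**Inputs**

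- From VII.B: improvement 70% on toxin and 20% on placebo; 30 women randomised, taken as 15 per arm; Fisher's exact test, two-sided, p<0.05.
- From IV.D: the third case stops the study. Cases after a second injection also count. At most two primary ratings can therefore be lost this way in a trial that runs to completion.
- Assumed, because the documents give no rate: each toxin woman has the event with probability q between 1% and 5%, always before the rating, and every affected woman goes unrated and is left out of the test.

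**Reproducing the plan's own figure**

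The usual two-proportion formula, with mean proportion 0.45 and difference 0.50, is

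n = [1.96 × √(2 × 0.45 × 0.55) + 0.8416 × √(0.70 × 0.30 + 0.20 × 0.80)]² / 0.50² = (1.379 + 0.512)² / 0.25 = 14.3

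This rounds up to 15. At 14 per group the same approximation gives 79.1% power, so the stated 14 per group at 80% is reproduced to within rounding. Exact Fisher power by enumeration is lower: 68.0% at 15 versus 15. That is the reference below.

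**Step 1: effect of k lost toxin ratings**

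All outcomes are enumerated (binomial in each arm). Then k of the 15 toxin women are removed, and the p<0.05 conclusion before and after removal is compared. Random loss is hypergeometric. The brackets remove only improved or only unimproved women.

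| Loss pattern | k = 1 | k = 2 |
|---|---|---|
| At random | 4.5% (all towards significance) | 8.6% (4.2% towards, 4.5% away, before rounding) |
| Only unimproved lost | 12.7% (towards) | 16.9% (towards) |
| Only improved lost | <0.001% | 9.7% (away) |

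An example of a change towards significance: 10/15 versus 4/15 gives p = 0.066, but with one unimproved toxin woman removed, 10/14 versus 4/15 gives p = 0.027.

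Power with random loss is 72% for k = 1 and 68% for k = 2, against 68% with none lost. The rise at k = 1 reflects the discreteness of Fisher's test.

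**Step 2: chance of losing one or two ratings, binomial(15, q)**

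| q | P(1) | P(2) | P(1 or 2) | P(3 or more) |
|---|---|---|---|---|
| 1% | 0.130 | 0.009 | 0.14 | 0.0004 |
| 5% | 0.366 | 0.135 | 0.50 | 0.036 |

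Three or more cases stop the study and are not counted.

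**Step 3: overall chance that the conclusion changes**

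P(1) × change at k = 1, plus P(2) × change at k = 2. For random loss:

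- q = 1%: 0.130 × 0.0450 + 0.009 × 0.0864 = 0.0067
- q = 5%: 0.366 × 0.0450 + 0.135 × 0.0864 = 0.0281

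The same sum gives 1.8% to 6.9% if only unimproved women are lost, and 0.1% to 1.3% if only improved women are lost.

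**The case against.** The strongest reply is that the event will hardly occur. IX.B.3 says sphincter weakness was not seen in the studies it cites, except in one woman with prior urinary incontinence, and IV.B excludes that history. A 5% rate, which would stop the trial on toxin-arm events alone in 3.6% of cases, fits poorly with that account. This stands: the upper end of the range is generous.

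The early contact names genitourinary infection and bowel or bladder change, not prolapse. The next scheduled gynaecological examination is at the one-month visit, where the response questionnaires are also completed. This stands too: loss before the rating is mainly a matter of self-reported incontinence.

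It can be argued that V.E's assessment comes first and IV.C is applied only afterwards. That is a workable reading, but the text does not state it, and IV.C remains unqualified.

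Other safeguards are partial. Section VIII tracks all adverse events within 6 weeks of injection, but that is not a pain rating. Randomising 30 against 28 required covers numbers, not loss related to arm. The consent form and the DSMB charter were not available and might address assessments after withdrawal.

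Finally, IV.C and IV.D together form a cautious safety rule. That caution is reasonable, but barring the second injection preserves it, and the investigator keeps discretionary withdrawal.

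**Conclusion.** The concern holds, at low severity. A rule followed as written can remove the primary rating of a woman with a possible toxin effect, after the only randomised dose has been given, and it is inconsistent with V.E.

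The expected size is small: 0.7% to 2.8% of conclusions changed under random loss, and 0.1% to 6.9% across the outcome-dependent brackets. These figures rest on the planned 70% versus 20%, 15 per arm, an assumed 1% to 5% event rate, every event falling before the rating, every affected woman unrated, and missing women excluded from the test. The last three event assumptions are all unfavourable to the plan. Average power is not the issue. The case for changing the text is that it removes a possible source of arm-related missing data at almost no cost.

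**What to change.** Replace the IV.C item with a rule that a woman with incontinence or prolapse after injection receives no further study injections, stays in follow-up, and completes the one-month improvement rating through the existing electronic survey or by telephone, unless she withdraws consent. Cross-refer V.E to this rule and keep its assessment step. Section IX.B.3 already uses this model for women who become pregnant after the one-month visit: they continue outcome assessments but cannot have the second injection.

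Leave the other IV.C criteria as they are, but ask for the one-month rating before exit where the woman is willing. A best-case and worst-case sensitivity analysis for any rating still missing is optional.

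The cost is one line in IV.C, a cross-reference in V.E, and a short rating for about two women at most. Sample size, primary test, stopping rule and safety reporting are unchanged, and the investigator can still withdraw a woman for safety under the existing adverse-event criterion.
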